Information was preferentially taken from documented medical records as preferred means (as it also mentioned the diagnosis associated with OCS administration) or second means, from the pharmacy records (no diagnosis); the third level of certainty was based on information provided by parents to the research coordinator with reports of the drug, posology and diagnosis. However, If self-reported information was not confirmed in the Medical records or Pharmacy report, information on the OCS was reviewed by an independant adjudicator with clinical expertise in asthma.

In the case of multiple exacerbations with OCS use, events were considered separate events if they were separated by 7 days or more. In cases where conflicting information was collected from different sources, or there were multiple reports within a short window of time clinical records were reviewed by the independent adjudicator to determine the number of separate events.

It was considered that there was OCS use if at least one dose of OCS was administered, prescribed or dispensed to the patient. This outcome was chosen because it is a clinically meaningful efficacy measure that has been shown to be important for family, health care providers, and payers, to influence practice, and the metric (counting all OCS per patient) was preferred by parents.

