Documented OCS events will be considered part of the study period if they were administered or prescribed after randomization (providing that the time of administration of OCS is documented after randomization and after the randomization visit, that is, was not prescribed on Med Examination at randomization (CRF “*Medical Examination*”, Q9. *Are you prescribing or recommending any systemic (oral, iv, im) corticosteroids today for the management of a CURRENT exacerbation?*, variable [medex_rec_sys_cort]). All OCS administered or dispensed on the day of randomization were reviewed by an independent adjudicator. OCS administered or prescribed throughout the study period were considered, including those administered or prescribed on the last day of the follow up period. The end of follow up window is defined as the date of visit 3 (CRF “*Discontinuation or End of study*”, variable [disendstud_last_sche_cont], 3. Date of last scheduled contact completed) or, if the visit 3 did not occur (e.g. lost to follow-up), at 7 months from the randomization date. As per the informed consent, the main outcome was meant to be obtained from medical and pharmacy records until the end of follow-up or at 7 months, even in participants dropped out or were lost to follow-up.

Detailed information on the coding of the primary outcome variable is provided in appendix 1.

Secondary outcomes

Detailed information on the coding and definitions for secondary outcome variables is provided in appendix 2.

Number of laboratory-confirmed respiratory infections per child

The number of laboratory-confirmed viral respiratory infections over the time frame of 7 months, quantified through a polymerase chain reaction (PCR) analysis of the nasal sample collected in clinic if the child was sick or by parents during colds and/or asthma exacerbations will be summarized for each child.

Number of reported viral infections

Total number of reported viral infection will be collected through verbal and written parental report (with each means of recording considered as a separate outcome).

Number of reported asthma exacerbations

Total number of reported asthma exacerbations will be collected through verbal and written parental report (with each means of recording considered as a separate outcome).

Number of acute-care visits / hospital admissions

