Appendix 1: Primary outcome variable coding

Primary outcome (OCS)

Suggested wording for use in manuscripts:

The primary outcome was number of short courses of systemic corticosteroids (OCS) prescribed for asthma during the 7-month intervention period, as confirmed by hospital and/or pharmacy records (or exceptionally, reported by parents and determined to be credible by an independent clinician).

Sources of OCS events

OCS could be documented in a number of places in the study CRFs including:

REDCap database:

- Med Examination CRF (to be considered administered or prescribed prior to randomization);
- Visit and Phone Contact CRF;
- CRF OCS in Medical Records (Clinic visit 1) – should contain info about OCS dated PRIOR to Randomization, to be verified in case any typos/mistakes have been done during the data entry;
- CRF OCS in Medical Records at end of study;
- CRF Pharmacy Report (Clinic visit 1) – should contain info about OCS dated PRIOR to Randomization, to be verified in case any typos/mistakes have been done during the data entry;
- CRF Pharmacy Report at end of study;
- CRF Additional cold or asthma flareup (main redcap).

REDCap3 database (parent-reported):

- CRF Cold and Asthma Flare Up Diary For Young Children;
- CRF Summary of an asthma flare-up or cold.

Validation of OCS events

Timing:

To be considered an outcome, an OCS must be administered or prescribed after randomization but could include the day of randomization, provided it was not prescribed on the MEDEX par the study physician and there was credible information of its administration/prescription after the time of rerandomization, until (and including) the last day of the follow up window. For the purposes of OCS use, the end of the follow up window is either the date of visit 3, or if the visit 3 did not occur, the randomization date plus 7 months.

Completeness of the data:

The complete information about OCS includes the name of the medication, dose, daily frequency, duration, and route as well as reason.

Relationship with an asthma exacerbation:

(1) Inclusion

- OCS use requires a medical documentation (MedRec CRF) or by the parental report (verbally recorded in VPC or on ADYC) that the reason for its use is asthma related, defined as:
 - i. Asthma flare-up, Asthma-like diagnoses (bronchospasm, airway hyperactivity, bronchiolitis, bronchitis, wheezing, pneumonia, etc.);

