 - ii. Other diagnosis (Pneumonia, Otitis) as such indication would suggest a co-existing diagnosis of asthma
 - iii. Unknown: Handling of unconfirmed reasons of OCS use. Unless otherwise confirmed, all OCS uses will be assumed to be for asthma (i.e., pharmacy dispensing of OCS without parental report or medical record of reason for use), given the high prior probability of this reason in included participants.

(2) Excluded:

- OCS administered for treatment of conditions or other respiratory conditions (e.g. cutaneous conditions, adrenal insufficiency, anaphylaxis (anaphylactic shock), kidney disease, serum sickness, surgery, croup' or 'laryngitis' etc.) as documented in eCRF OCS documented in the medical Record (1st priority), Visit and phone contacts (less priority as self-reported) or ADYC will be excluded. Of note, if prescribed in Med examination (eCRF), then it is clearly for asthma.

Handling of Special cases

Denied administration of prescribed or dispensed OCS by parents:

If parents deny administration of identified OCS prescribed or dispensed by pharmacy, the OCS will be counted as an OCS use for the primary outcome, as per the physician intention for the child to use OCS, as this intention is the marker of moderate or severe exacerbation. (qu 10 et 11)

Delayed administration of prescribed or dispensed OCS by parents

If parents credibly report of an alternate start date than that documented in pharmacy records (for example, medication dispensed ahead of time for subsequent use as part of an action plan or prior to travel), the actual date of OCS use will be reported by parents in VPC CRF (or ADYC), and this date will be considered for primary outcome calculation. Such credible report should be documented in VPC CRF by the nurse. In this case, the concordance between the information provided verbally (VPC) or in writing (ADYC) by parents regarding the reason for, and information about, the OCS prescription will be cross-verified with the documentation of the original prescription in med records CRF (reason, name and dosage)—preferred approach—and/or Pharmacy report (OCS name, dose, duration)—secondary approach as the Pharmacy report that does not provide the reason for its prescription. If

the date of initiation has not occurred before or at Visit 3, the OCS would not be considered as OCS use during the study period. (qu 10.2.6.2)

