If **pharmacy records were never obtained**, we will consider accepting the OCS medications as described in the Clinic and Phone contacts eCRF, provided that the information is considered credible by the nurse and the reported reason is concordant with other document (med records or parental report) about the OCS.

Of note, given the potential subjectivity of the judgement of 'credibility', these approaches will be independently coded by two biostatisticians, to identify any rule resulting in discrepancy. Any rule resulting in discrepancies will be identified; and all OCS events in which these rules applied would be independently assessed by an independent adjudicator, whose decision will be final.

[Events with multiple 'courses'](#)

Each record of a possible OCS course will be extracted from the CRFs and added to a long file with a source, reason for administration, type of documentation, start and end date.

Once all CRF sources have been extracted, OCS courses will be evaluated to determine if they represent one event or multiple events.

Any occurrence of two or more 'courses' (whether administration, prescription, dispensing, or parent-administered), initiated with a 7-day period (between the beginning of 1st course and the beginning of the 2nd course) or within a 2-day period (between the end of a 1st course and the beginning of the 2nd course) which ever if longest, will be counted only once (and assumed to be for the same exacerbation). These approaches will be independently coded by two biostatisticians, to identify any rule resulting in discrepancy. Any rule resulting in discrepancies will be identified; and all OCS events in which these rules applied would be independently assessed by an independent adjudicator, whose decision will be final.

Following the double-coding approach, the team of [name] will prepare the list of documented OCS, in a wide format, showing all sources of OCS reporting:

- Medical Examination,
- OCS in Medical records,
- Pharmacy Report
- Visit and Phone Contact,
- Additional cold and asthma flare-up (ACAFU)
- Asthma Flare-up Diary for Young Children (ADYC) (REDCap3)
- Summary of an asthma flare-up or cold (SAF) (REDCap3)

The information from REDCap3 (ADYC and Summary CRF) will be merged with the main list of the OCS to detect special cases when information is credibly reported in REDCap3, but missing in REDCap main database.

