1.1.6 Total number of doses administered or given to parents by health care provider (for example include a dose of dexamethasone to give at home by parents) [ocsdoc_end_nb_dos] # doses	text	Should not be a missing value
1.1.7 Was the dose accompanied by a prescription (to be filled by community pharmacy), as documented in the medical chart? [ocsdoc_end_pres]	1Yes 0No	Should not be a missing value
1.1.7.1 Date of prescription[ocsdoc_end_pres_date]	text (date_ymd), Required	Should not be a missing value
1.1.7.2 Medication (Use the generic name(s), NOT trade name(s)): [ocsdoc_end_pres_med]	1Prednisone tablet 2Prednisolone (Pediapred®) 3Dexamethasone (solution or tablet) 4Methylprednisolone (solution or tablet) 5Solu cortef 6Other	Should not be a missing value
1.1.7.2 a) If other, specify[ocsdoc_end_pres_med_oth]	text	Should not include hydrocortisone or other unrelated medications
1.1.7.3 Route[ocsdoc_end_pres_route]	1Oral 2IV 3IM	Should not be a missing value
1.1.7.4 Total daily dose in mg[ocsdoc_end_pres_tot_mg]	text	Should not be a missing value

mg		
1.1.7.5 Prescription duration (# days) [ocsdoc_end_pres_dur] days	text	Should not be a missing value

Comment: the same coding should be applied to information about Medication 2 (Q1.2.1 - Q1.2.7.5) and Medication 3 (Q1.3.1 - Q1.3.7.5).

Pharmacy Report / End of Study CRF

Variable / Field Name / Field Label	Field Attributes (Field Type, Validation, Choices)	Required
Section Header: Oral Corticosteroids (OCS) Medication	1 Yes 0 No	Should be Yes
1. Has there been any serving of oral corticosteroids (OCS) medication since randomization until V3 (or 7 months after randomization if premature discontinuation) ? [pharm_ocs_end]		
1.1.1 Date of dispensing [pharm_ocs_end_dat_disp_1]	text (date_ymd), Required	Should not be a missing value
1.1.2 Medication (use the generic or trade name) [pharm_ocs_end_nam_1]	1 Prednisone tablet 2 Prednisolone (pediapred) 3 Dexamethasone (solution or tablet) 4 Methylprednisolone (solution or tablet) 5 Other (specify DIN)	Should not be a missing value
1.1.2 a) Specify [pharm_ocs_end_nam_1a]	text	Should not include hydrocortisone or other unrelated medications

1.1.4 mg per dose [pharm_ocs_end_dos_1] mg	text, Required	Should not be a missing value
1.1.5 Frequency (#times/day) [pharm_ocs_end_freq_1] #times/day	text	Should not be a missing value
1.1.6 Prescription duration (#days) [pharm_ocs_end_dur_1] days	text	Should not be a missing value

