1.1.7 Date of the prescription [pharm_ocs_end_date_1]	text (date_ymd), Required	Should not be a missing value

Comment: the same coding should be applied to information about Medications 2 - 6 (Q1.2.1 - Q1.2.7; up to Q1.6.1 - Q1.6.7).

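### The primary-outcome timing rule leaves out dispensing that the definition counts, and the merging rule can count one late-filled prescription as two exacerbations

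*SAP*

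**What the plan says.** All references are to the SAP.

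- **Definition** (Outcome(s), Primary outcome): "It was considered that there was OCS use if at least one dose of OCS was administered, prescribed or dispensed to the patient".
- **Timing, main text** (same section): "Documented OCS events will be considered part of the study period if they were administered or prescribed after randomization". Dispensing enters the timing text only for a single day: "All OCS administered or dispensed on the day of randomization were reviewed by an independent adjudicator".
- **Timing, Appendix 1** (Validation of OCS events): "To be considered an outcome, an OCS must be administered or prescribed after randomization". Dispensing is again not named.
- **Dispensing treated as countable elsewhere in Appendix 1.** Under Relationship with an asthma exacerbation, an unexplained fill is presumed to be for asthma; the example given is "pharmacy dispensing of OCS without parental report or medical record of reason for use". Under Handling of Special cases, a dispensed course counts even if the parents deny giving it. The end-of-study pharmacy form asks "Has there been any serving of oral corticosteroids (OCS) medication since randomization until V3".
- **Merging** (Appendix 1, Events with multiple 'courses'): two or more courses count once if they start within 7 days of each other, or if the second starts within 2 days of the end of the first, whichever window is longer. The kinds of course covered are described as "whether administration, prescription, dispensing, or parent-administered), initiated with a 7-day period".
- **Dates** (Appendix 1, CRF specific coding rules): a medical-record course that was only prescribed starts on the prescription date. For the end-of-study pharmacy report the rule mentions a date without saying which. That form holds the date of dispensing (item 1.1.1) and also "1.1.7 Date of the prescription".

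**The concern.** Two sets of rules for the primary endpoint do not fit together. The definition and several coding rules accept a dispensing as an OCS event, while both statements of the timing rule leave it out. The unnamed pharmacy date adds to this, because the choice of date decides whether a record falls in the study period and which records it merges with.

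The merging rule treats a prescription and its own fill as two courses and joins them only if their dates are close. Appendix 1 itself foresees OCS obtained ahead of need for an action plan or travel, so gaps between prescribing, dispensing and use are to be expected.

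At stake are the primary count, the mean difference that the SAP says will be reported, and some precision, in a trial that recruited 323 of a planned 865 children.

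**Working it through.** The SAP states no figure on this point, so there is none to reproduce. The check applies the written rules to constructed records. Day 0 is randomisation in step 1 and the date of prescription in step 3.

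**1. Timing.** Take a prescription dated day −20, dispensed on day +30, with no record of administration.

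- Definition: a dispensing occurred on study, so this is OCS use.
- Timing rule: there is no administration after randomisation, and the prescription came before it, so the record is outside the study period.

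The same record gives 1 event under one rule and 0 under the other. All three conditions are needed: an earlier prescription, an on-study fill and no administration record. A fill of a prescription written on study, or one with documented on-study administration, passes both rules.

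**2. Pharmacy date.** With item 1.1.1 as the start, the record above starts on day +30. With item 1.1.7 it starts on day −20. The special-case rule on delayed use, and item 10.2.6.2 of the visit and phone form, suggest that dispensing is the default, but no coding rule says so.

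**3. Merging.** A medical-record prescription of *d* days written on day 0 ends on day *d* − 1. A fill on day *s* merges if *s* is within 7, or if *s* − (*d* − 1) is within 2. 'Within' can be read as strict or inclusive, so both are shown.

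| Course length *d* | First fill day counted as a second event (strict) | (inclusive) |
|---|---|---|
| 1 to 5 days | 7 | 8 |
| 7 days | 8 | 9 |
| 10 days | 11 | 12 |

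Example: a 5-day prescription written on day 0 and filled on day 10. Start to start is 10 days; end to start is 10 − 4 = 6 days. Neither window applies, so one prescription yields two events. The main text, which separates events 7 or more days apart, gives the same answer.

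The fields that would link the pair exist on both sides: item 1.1.7.1 of the medical-record form and item 1.1.7 of the pharmacy form. No rule uses them to pair a fill with its prescription before merging.

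**4. Effect on the analysis.** The error fraction *f* is an assumption, equal in both arms, with Poisson true counts.

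- Double counting: each true event contributes 1 with probability 1 − *f* and 2 with probability *f*. The mean is multiplied by 1 + *f*, the variance of the count by 1 + 3*f*, and var(log IRR) by (1 + 3*f*)/(1 + *f*)².
- Loss: the mean is multiplied by 1 − *f*, and var(log IRR) by 1/(1 − *f*).

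| *f* | var(log IRR), double counting | var(log IRR), loss |
|---|---|---|
| 2% | × 1.019 | × 1.020 |
| 5% | × 1.043 | × 1.053 |
| 10% | × 1.074 | × 1.111 |

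The expected rate ratio does not move. With the targeted 25% reduction and *f* = 3%, (0.75 × 1.03)/(1 × 1.03) = 0.75. The mean count in each arm and the mean difference are scaled by 1 + *f* or 1 − *f*.

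**The case against.** The strongest reply is that the SAP already has safeguards and that its other text shows the intent.

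- **Delayed use.** Where parents credibly report a different start date, that date replaces the pharmacy date, and the report is cross-checked against the original prescription. This stands where parents report. It does not help where they do not, and it does not say that the medical-record row is re-dated or removed.
- **Adjudication.** The main text sends conflicting sources, and multiple reports in a short but undefined window, to an independent adjudicator who sets the number of events. That will catch some cases, but a prescription and a fill 10 days apart need not trigger it. The adjudication in Appendix 1 starts from a discrepancy between two biostatisticians, and two coders who apply the same date rule will agree on the same double count.
- **Intent.** The pharmacy form, the presumption of asthma and the listing of dispensing as a course all point to counting fills. So the timing rule is better read as inconsistent wording than as an instruction to drop records. That is fair, but coders work from the wording.
- **Repeats.** Linking every fill to its prescription would merge genuine repeats: a prescription filled on day 0 and again on day 60 for a new exacerbation carries one prescription date. This stands, and it limits the remedy to the first fill.

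A reader might also infer that false second events pull the rate ratio towards 1. That would follow if the same absolute number were added to each arm: adding 3% of the control mean gives (0.75 + 0.03)/(1 + 0.03) = 0.757. But a false second event is the late fill of a prescription already counted, so it scales with each arm's own events. The SAP offers no mechanism for equal absolute additions.

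**Conclusion.** The point holds as a contradiction between stated rules for the primary endpoint. An on-study dispensing against a pre-randomisation prescription, with no administration record, is in under the definition and out under the timing rule. The pharmacy start date is not named. One prescription first filled more than about 7 days later, and more than 2 days after its nominal end, counts twice unless a parental report or adjudication steps in.

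Its size cannot be derived from the SAP. The likely result is a small number of miscounted events, similar in both arms if coding is blinded, with a modest loss of precision and a distorted mean count and mean difference. The range in the working rests on assumed error fractions of 2% to 10%, Poisson counts and equal rates by arm.

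Two stronger readings are not supported: that pharmacy refills in general are lost, and that the rate ratio is biased towards 1.

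**What to change.** Before unblinding:

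1. **Timing and dates.** Use one list of qualifying acts (administration, prescription, dispensing) in the definition and in both statements of the timing rule. For pharmacy-source records, name the dispensing date (item 1.1.1), or the credible parent-reported start, as the start date. Send on-study fills of prescriptions dated before randomisation to the existing independent adjudicator. Without that review, adding dispensing to the list would let in late fills that belong to an exacerbation before randomisation.
2. **Linking.** Before applying the 7-day and 2-day windows, link only the first fill to its source prescription through the dates already held (medical-record item 1.1.7.1, pharmacy item 1.1.7). Count that pair once unless the adjudicator finds a separate exacerbation. Leave later repeat fills to the date windows.

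The cost is a few sentences in the Primary outcome section and Appendix 1, one matching step in the code, and adjudicator time for the flagged records. No new data are needed.

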Family expenses during exacerbations associated to medications, ED visits, hospitalisations, as well as income loss were recorded at each study contact (phone or visit) by research nurses. The total amount of expenses reported during follow up will be summarized for each child.

Health care cost

Health care cost, calculated by assigning unit costs to ED visits, hospital admissions, medication use, and physician visits whereas the cost of intervention was determined through drug manufacturer, nursing time, and facility's resources, documented in a random sample of 100 children.

Severity of asthma symptoms

The sum of the daily scores as a measure of the severity of asthma symptoms during exacerbations, completed daily by parents using the validated 17-item, each scored from 1 (best) to 7 (worst), Asthma Flare-Up Diary for Young Children symptoms (ADYC) and standardized over 7 days using the method published in [name] et al 2016.

Intensity of use of rescue B2-agonists

Intensity of use of rescue β 2-agonists during asthma exacerbations, defined as:

- Cumulative rescue bronchodilator use: \sum daily number of puffs from the first day until last day of use until last day of use, inclusively. Units [puffs/episode]
- Average rescue bronchodilator score = Cumulative rescue bronchodilator use \div duration of use, units [average puffs/day]

Parental functional status

This is a measure of the parental report of how much he/she was affected by each asthma flare up reported (i) on the Effect of a Child Asthma flare-up on Parents (ECAP) comprising 21 questions, where the ECAP score for each episode is the mean of values for non-missing items collected on a seven-point scale (1 :Not at all to 7 : Extremely) and (ii) as Global parental functional status, on a 7-point likert scale to the question *Overall, how much did this asthma flare-up affect you?* Each means of recording is considered as a separate outcome. Only one parent is surveyed for each flare-up.

Subgroups

Subgroups of interest were chosen based on the potential for the response to vitamin D to vary by baseline characteristics that are hypothesized to modify the effect of vitamin D on asthma related outcomes. These subgroups were defined based on the values of the baseline covariates. Detailed

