- Mean duration of use of β 2-agonist was used during each cold/asthma flare-up reported verbally or documented on the validated written 'Asthma Flare-up Diary for Young Children' over the time frame of 7 months (with each means of recording considered as a separate outcome).
- Mean of out-of-pocket asthma related expenses per exacerbation
- The sum of the daily ADYC scores as a measure of the severity of asthma symptoms during exacerbations, completed daily by parents using the validated 17-item, each scored from 1 (best) to 7 (worst), Asthma Flare-Up Diary for Young Children symptoms (ADYC) and standardized over 7 days
- Mean intensity of β 2-agonist use reported on the diary as
 - Cumulative rescue bronchodilator use: \sum daily number of puffs from the first day until last day of use until last day of use, inclusively. Units [puffs/episode]
 - Average rescue bronchodilator score = Cumulative rescue bronchodilator use \div duration of use, units [average puffs/day]
- Mean parents' functional status during exacerbations per child
 - Reported as the mean ECAP score
 - Reported as Global functional status on a 7-point likert scale from 1-not at all, to 7-extremely

Primary Efficacy Analyses

A Poisson regression model, will be estimated, using an ITT approach, including only randomization group as a predictor and adjusting only for the stratification of randomization by clinical site. This model will be used to estimate the incidence rate ratio comparing the mean number of oral corticosteroids (OCS) per child during the 7-month follow-up by study group. If overdispersion is present, a negative binomial model will be used. If there are large variations in person-time an adjustment using an offset term will be made. Two sensitivity analysis are planned; 1) the incidence rate ratio will be stratified by the month of recruitment to explore the possibility of effect modification by seasonality and 2) the incidence rate ratio will be stratified by year of the pandemic (2000-2001) to assess the possibility of effect modification by exposure to the COVID-19 pandemic period. The original analysis plan included a fixed effect for each site. However, for sites with a very small number of recruited patients, these small sites may be grouped together.

Secondary outcome analyses

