REDCap3, CRF Effects of a Young Child's Cold or Asthma Flare-up on Parents(ECAP), completed by parents after each exacerbation.

- Q 23. How many days of work or regular planned activities did you miss because you had to take care of your child? **[aep_days_work]**
- Q 24. To what extent were you able to go about performing your work or regular planned activities? **[aep_ext_perf_percent]** (0-100%)

Family expenses

Family expenses during exacerbations associated to medications, ED visits, hospitalisations, as well as income loss were recorded at each study contact (phone or visit) by research nurses. The total amount reported during follow up will be summarized for each child as the sum of all amounts reported on the following CRFs:

REDCap, Visit and Phone contact CRF (Section 6):

[phcon_expenses] 6. Have there been any out-of-pocket expenses related to your child's colds or asthma flare-up since the last contact? (Yes/No)

[phcon_expenses_y] 6a. Specify any expenses for (choose all that apply)

1. Prescription drugs Médicaments sur ordonnance;
2. Non-prescription medication/product Médicaments ou produits sans ordonnance;
3. Transport to or parking at medical care facilities Transport ou stationnement aux centres médicaux.

[phcon_insur_cover] 6.2 Did a public or private drug insurance help cover part of the cost of this medication? (Yes/No)

Health care cost

Health care cost, calculated by assigning unit costs to ED visits, hospital admissions, medication use, and physician visits whereas the cost of intervention was determined through drug manufacturer, nursing time, and facility's resources, documented in a random sample of 100 children.

Severity of asthma symptoms

The sum of the daily scores as a measure of the severity of asthma symptoms during exacerbations, completed daily by parents using the validated 17-item, each scored from 1 (best) to 7 (worst), Asthma Flare-Up Diary for Young Children symptoms (ADYC) and standardized over 7 days using the method published in [name] et al. 2016.

Parents are asked to record any asthma symptoms child has experienced during the past 24 hours, the diary should be completed every evening from the first day of cold symptoms until 2 days with no asthma symptoms.

Data source: REDCap3 – written parental report, CRF “Cold and Asthma Flare Up Diary For Young Children (ADYC)”

Q1 - Q7, the Symptoms over last 24 hours:

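### Family expenses are defined as a total per child including income loss, but the only listed by-arm summary is out-of-pocket cost per exacerbation, and the listed source items show no income-loss category

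*SAP*

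**What the plan says.** Family expenses is a named secondary outcome, and the SAP describes it in three places.

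- **Secondary outcomes, Family expenses.** The content is given as "Family expenses during exacerbations associated to medications, ED visits, hospitalisations, as well as income loss were recorded at each study contact", and the unit as "The total amount of expenses reported during follow up will be summarized for each child".
- **Appendix 2, Family expenses.** The same content sentence is repeated, followed by the derivation: "The total amount reported during follow up will be summarized for each child as the sum of all amounts reported on the following CRFs". The only source then listed is Section 6 of the Visit and Phone Contact form. Its opening question is "Have there been any out-of-pocket expenses related to your child's colds or asthma flare-up since the last contact? (Yes/No". Three categories follow: "Prescription drugs Médicaments sur ordonnance", "Non-prescription medication/product Médicaments ou produits sans ordonnance" and "Transport to or parking at medical care facilities Transport ou stationnement aux centres médicaux". A yes/no item on drug insurance comes last.
- **Descriptive analysis of primary and secondary outcome measures.** In the list of measures to be summarised overall and by arm, the expense entry is "Mean of out-of-pocket asthma related expenses per exacerbation".

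Work missed by parents is recorded in Section 7 of the same form. In the SAP it serves a separate secondary outcome, lost parental workdays, which is counted in days.

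**The concern.** The definition and the listed by-arm summary differ in unit (child against exacerbation) and in content (including income loss against out-of-pocket only). The derivation in Appendix 2 also names source items that do not show every component of the definition.

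The unit matters because the trial looks for a benefit through fewer exacerbations. A mean per exacerbation is computed only where an exacerbation occurred, which is after randomisation and may depend on treatment. It is therefore not a comparison of all randomised children, although the SAP's analysis sample is all 323 of them. The content matters because a programmer working from Appendix 2, which the SAP presents as the detailed coding source, could build a variable that lacks a component its own definition includes.

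**Working it through.** The SAP states no family-cost figure, so there is none to reproduce. The check is a comparison of the texts, followed by one identity.

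**1. Side by side**

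| Place in SAP | Unit | Income loss |
|---|---|---|
| Secondary outcomes, Family expenses | Total per child over follow-up | Included |
| Appendix 2, definition sentence | Total per child over follow-up | Included |
| Appendix 2, listed Section 6 items | Amounts since last contact, to be summed | No such category shown |
| Descriptive analysis list | Mean per exacerbation | Out-of-pocket only |

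The first two rows agree. The last row departs in both unit and content. The third row does not show a component that the first two include.

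**2. What the unit does.** For expenses attributed to exacerbations,

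mean expense per child = mean exacerbations per child × mean expense per exacerbation.

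Taking ratios of vitamin D to placebo,

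per-child ratio = exacerbation rate ratio × per-exacerbation cost ratio.

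The SAP's primary objective gives a 25% relative reduction, so a rate ratio of 1 − 0.25 = 0.75. That target concerns exacerbations treated with oral corticosteroids. Applying it to all costed episodes is an assumption made only to show the mechanism. The cost ratios below are also assumed.

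| Assumed cost ratio per exacerbation | Per-child ratio |
|---|---|
| 0.80 | 0.75 × 0.80 = 0.60 |
| 1.00 | 0.75 × 1.00 = 0.75 |
| 1.33 (4/3) | 0.75 × 4/3 = 1.00 |

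In the middle row the per-exacerbation summary shows no difference while the cost per child is a quarter lower. In the last row it shows an increase of a third while the cost per child is equal. A child with no exacerbation adds zero to the per-child mean and nothing to the per-exacerbation mean.

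**3. Fit of the per-exacerbation mean to the data.** The Section 6 question covers the interval since the last contact, and it covers colds as well as asthma flare-ups. A per-exacerbation figure therefore needs a rule for assigning interval amounts to exacerbations, and the SAP gives none. A per-child total needs no such rule.

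**4. Income loss.** If income loss is a share s of the defined family cost, a sum without it captures 1 − s. The SAP gives no value of s. An assumed range of 0.10 to 0.75 gives 0.90 to 0.25, which only restates the assumption. Section 7 does not fill the gap as written, because its outcome is in days and no rule turns days into money.

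**The case against.** The case on the other side has four parts.

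- **The per-exacerbation mean is one descriptive entry.** The definition and Appendix 2 agree on the per-child total, and the descriptive section does not redefine outcomes. The Secondary outcome analyses section opens with a general rule that secondary outcomes follow the primary modelling strategy, and its lists of examples are not exhaustive. This stands. A reader might infer that the SAP has no between-arm analysis of the per-child total, but the general rule covers it. What remains is that the only expense summary actually listed by arm has a different unit and content from the outcome.
- **The form excerpt is visibly abbreviated.** It runs from 6 and 6a to 6.2 with no 6.1, and shows no field for an amount although amounts are to be summed. The Section 7 items are also shortened. This stands too. A reader might infer that income loss was not collected or will certainly be left out, but the excerpt cannot prove that, and the SAP says it was recorded. The supportable statement is that no source for it is named.
- **Other outcomes show frequency and work absence.** Exacerbations, acute-care visits and lost workdays are each reported. That is true, but they do not give family expense.
- **The economic evaluation is separate.** The Ancillary studies section mentions family cost but does not tie it to either version of this outcome. An effect on the cost-effectiveness result therefore cannot be claimed.

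**Conclusion.** The point holds as an inconsistency within the SAP. The outcome is a per-child total including income loss. The one by-arm expense summary listed is out-of-pocket cost per exacerbation, which leaves out children without exacerbations and cannot reflect savings from having fewer. A sum coded from the listed Section 6 items alone would also lack income loss.

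It would go too far to conclude that the trial's family-cost result is wrong, or that family cost would fall by 25%. The target concerns only exacerbations treated with oral corticosteroids, whereas Section 6 covers all colds and flare-ups. The contrast of 0.75 with 1.00 illustrates the mechanism under stated assumptions and is not an estimate. No size of understatement from income loss can be given from the documents. The primary outcome, safety analyses and error control are not affected.

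**What to change.** 1. In the descriptive analysis list, replace the expense entry with total family expense per child over follow-up, by arm, with zeros included, so that it matches the definition and Appendix 2. If a per-exacerbation mean is kept, label it as an additional description only.
2. In Appendix 2, either name the field that holds the income-loss amount and add it to the sum, or remove income loss from the definition there and in the Secondary outcomes section, leaving work absence to the lost-workdays outcome. Multiplying lost workdays by a unit value is less attractive: it would use the same data in two outcomes and assume that missed days were unpaid, which the SAP does not say.

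The cost is SAP wording and at most one derived variable. No new data are needed if the income-loss amounts were recorded as the SAP states, or if the term is dropped.
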